### 5.3.2. Covariates

The list of demographic and clinical characteristics considered for descriptive reporting, subgroups and inclusion as covariates in models for generating the propensity scores are provided in Table 5.3. The Komodo Health database will be source of all variables.

Patients will be considered to have a comorbidity or hospitalization during baseline if there was evidence of a diagnosis at any time during the baseline period. Evidence of comorbidities or hospitalization during follow-up will be considered as new diagnoses. Once diagnosed, patients will be considered diagnosed for the remainder of their follow-up. ART adherence during baseline and follow-up will be updated every 6 months (180 days) based on the data collected in that previous timeframe. For baseline annual physical exam and annual influenza vaccine, patients will be considered adherent (coded as 'Yes') if there was evidence of these events at any time during the baseline period. During the follow-up, patients will be considered adherent up to 365 days after the last event date.

For annual CD4 and viral load laboratory tests during baseline and follow-up, patients will be coded as 'Yes' up to 365 days after the last event date. For respiratory virus season during follow-up, patients will be coded as 'Yes' if the observation time is in October, November, December, January, February, March or April.

The baseline period for the assessment of covariates is the six months prior to the index date, i.e., no data prior to six months will be included.

Covariates used at baseline only will be considered time-fixed confounders. Covariates additionally or only used during follow-up will be considered time-varying confounders.

Categories may be collapsed, or covariates may be excluded from the propensity scores if models fail to converge.

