#### **5.8.4. Inverse Probability of Treatment Weighting for Time-Varying Exposures**

Except for patients vaccinated more than 13 days before the end of the baseline period, exposure (vaccination) status will not be fixed at start of follow-up, with patients able to receive PCV13 during follow-up. Therefore, PCV13 will be considered a time-varying exposure. The values for some clinical characteristics may also change during the study period and values during baseline may be poor proxies for covariate values at the various points during the follow-up. Therefore, some covariates will be treated as time-varying confounders (Section 5.3.2).

Inverse probability of treatment weighting (IPTW) will be generated from predicted probabilities of vaccination status (propensity scores) to create pseudo-populations where any imbalances in the potential confounders by vaccination status are reduced. For the analyses of first events, stabilized weights will be generated for each patient for the baseline period and every 30 days from index during the follow-up until the earliest of the following: outcome, death, end of health plan enrollment or end of study period. For the analyses of recurrent events, stabilized weights will be generated for each patient for the baseline period and every 30 days from index during the follow-up until the earliest of the following: death, end of health plan enrollment or end of study period. This aims to make vaccination status independent of the measured confounders at each of the follow-up timepoints [9]. The weights will be used to estimate the average treatment effect (ATE). For the analysis of RZV, stabilized weights will be generated every 90 days instead of 30, due to the expected lower numbers of patients vaccinated with RZV overall and in each interval.

The numerators for the stabilized weights will be the estimated probability of a patient's observed vaccination status at timepoint given their prior vaccination status and time-fixed covariates. The denominators will be the estimated probability of a patient's observed vaccination status at the given timepoint given their prior vaccination status, time-fixed covariates and time-varying covariates. Numerators and denominators after vaccination will be set to 1 and the cumulative product of these ratios will be calculated, therefore IPT

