weights after vaccination will be constant. Time-varying covariates will be lagged, i.e., within each 30-day (or 90-day for RZV) interval the vaccination status will be the status at the end of the interval, whereas the values for the covariates will be from the end of the previous interval. Cox proportional hazards models will be used to model the associations between vaccination status and the numerators and denominators.

It is possible that censoring may be informative, with patient characteristics associated with loss to follow-up. Therefore, patients who are censored may have different risks of the study outcomes than patients who are not censored. Inverse probability of censoring weighting (IPCW) will also be generated during the follow-up using the above methods for IPTW. These weights will be multiplied by the IPT weights to produce a new set of weights [9].

Distributions of the IPT, IPC and IPT\*IPC weights will be summarized by vaccination status. In the presence of extreme/outlier weights, stabilized weights may be truncated at the 1st and 99th percentiles for use in the Cox models for the outcomes. Although there is no formal definition of an extreme weight, the need for truncation will be judged based on the distributions and the potential effect on the interpretation of results [9].

Weights for first and recurrent events will be generated separately in datasets created for each study outcome; however, all weights will be derived without assessing their impact on the VE estimates. Weights will also be generated again in each of the subgroups. The weights will be generated using the *ipwtn* function within the *ipw* R package [10]. Example R code is provided in Appendix 7.2.

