#### **5.8.5. Assessment of Covariate Balance**

Standardized mean differences (SMD) will be calculated for the baseline period and every 30 days (or 90 days for RZV) since index for each of the covariates up to any PCV13 vaccination before and after the IPTW. Overall SMDs will be presented for each covariate before and after the IPTW (such as median and maximum values across the intervals with at least 100 patients vaccinated), as well as those at the end of each year of follow-up (at 360, 720, 1080, 1440, 1800, 2190, 2550, 2910 days). SMDs  $\leq 0.1$  will be considered as evidence of negligible imbalance. Variables with SMDs  $> 0.1$  after IPTW may be added to final weighted outcome models.

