#### **5.8.7. Vaccine Effectiveness**

Crude PCV13 VE percentages will be estimated based on  $(1-HR) \times 100$ , where HR is obtained from unadjusted Cox models for first episodes for each outcome. VE percentages will also be obtained from marginal structural Cox models (Cox-MSM) after applying the IPT and the IPT\*IPC weights. As the numerators for the stabilized weights will include the index-fixed covariates, those covariates will also be included in the Cox-MSM for the outcomes [9]. Cluster robust standard errors will be used to account for the multiple records per patient. The proportional hazards assumption will be assessed graphically with the inspection of Schoenfeld residuals.

To explore potential changes in VE over time, HRs may also be generated during specific time periods using piecewise Cox models. The time periods will be 0-3 years (0 to 1079 days), 3-5 years (1080 to 1799 days), 5-7 years (1800 to 2549 days).

VE may also be assessed for recurrent events using the Andersen-Gill (AG) model [11]. For each outcome, subsequent events will be of the same type, e.g., in the analysis of IPD it will be assumed that a patient is only at risk for future IPD events. The VE is assumed constant across the recurrent events.

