### 7.2.5. Code for Cox Models

```
#Code is the same for first event and recurrent events (Andersen-Gill) models
#Crude overall
library(survival)
crude.cox<-coxph(Surv(tstart, tstop, ipd) ~ pcv13 + cluster(ptid), data = ipdfirst)
```

```
#IPT weighted overall
iptw.cox<-coxph(Surv(tstart, tstop, ipd) ~ pcv13 + x1 + x2 + cluster(ptid),
                  data = ipdfirst), weights = iptw.stab
```

```

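### The SMD > 0.1 rule in SAP 5.8.5 can change the outcome model only by adding time-varying covariates, and it does not bar their post-vaccination values

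*SAP*

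**What the plan says.** - **The rule.** SAP 5.8.5 calculates SMDs "for each of the covariates up to any PCV13 vaccination before and after the IPTW", treats values up to 0.1 as negligible, and says that variables above 0.1 "after IPTW may be added to final weighted outcome models". It does not say which value of the variable would be entered, or which SMD (median, maximum or yearly) counts.
- **Fixed covariates.** SAP 5.8.4 builds the weight numerators from the probability of the observed vaccination status "given their prior vaccination status and time-fixed covariates". SAP 5.8.7 therefore states that "those covariates will also be included in the Cox-MSM for the outcomes". The example code in SAP 7.2.5 agrees: "coxph(Surv(tstart, tstop, ipd) ~ pcv13 + x1 + x2 + cluster(ptid", with no time-varying term.
- **Time-varying covariates.** SAP 5.3.2: "Covariates additionally or only used during follow-up will be considered time-varying confounders". In Table 5.3 this covers hospitalization, opportunistic infections, ART adherence, the comorbidities and others. For comorbidity and hospitalization, "Once diagnosed, patients will be considered diagnosed for the remainder of their follow-up".
- **Timing.** Within each weighting interval, "the values for the covariates will be from the end of the previous interval" (SAP 5.8.4). First-event records end at the outcome; recurrent-event records continue past it.

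**The concern.** A marginal structural model handles time-varying confounders through the weights so that they need not appear in the outcome model. The reason is that such variables can be both confounders of later vaccination and consequences of earlier vaccination. Putting their current values into the outcome model blocks any part of the vaccine effect that runs through them and can open collider paths through unmeasured frailty.

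The rule in SAP 5.8.5 permits this as the remedy for residual imbalance. Weights are also rebuilt for each outcome and each subgroup (SAP 5.8.4), so different VE estimates could end up conditioning on different variables and no longer estimate the same quantity.

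**Working it through.** The documents give no figure for this rule, so there is none to reproduce. The check has two parts.

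**1. What the rule can add**

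- A fixed covariate sits in both numerator and denominator of the stabilized weight, so weighting does not balance it. The SMD check will tend to flag fixed covariates by design, but adding them changes nothing because they are already in the model.
- What remains is the set classed as time-varying. Their baseline values are not listed as separate fixed terms in the SAP.
- The example dataset in SAP 7.2.1 holds these covariates only as time-updated columns. Patient 1001 becomes vaccinated in the interval from day 30 to day 60, and the time-varying columns continue to day 87. A programmer following the example would enter those columns.
- Table 5.3 defines hospitalization as any inpatient claim. Admissions for the outcome are not excluded, although pneumocystis codes are removed from opportunistic infections in the all-cause pneumonia analysis.
- In the recurrent-event analysis, a pneumonia admission therefore sets a permanent flag that would be conditioned on for later episodes.
- In the first-event analysis, records stop at the outcome and covariates are lagged. The issue there is consequences of vaccination. For example, in the IPD analysis an admission for a vaccine-preventable pneumonia lies on the path from vaccine to IPD.

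**2. Illustrative size**

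Inputs from SAP 5.2.3:
- all-cause pneumonia 5,487 and IPD 183 per 100,000
- VE 15% and 22.5% respectively
- 32% vaccinated (about 30% in the calculation)
- 4% annual censoring and 97 months of follow-up

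Assumed, because the documents do not give them:
- rate ratio for a latent frailty, 1 to 10
- rate ratio after hospitalization, 1 to 5
- share of pneumonias hospitalized, 0.3 to 0.8
- vaccine hazard ratio on pneumonia in the IPD scenario, 0.55 to 0.95
- rate ratio on vaccination of 2.0 for a fixed covariate and 1.5 for hospitalization

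Method: a deterministic large-sample monthly multistate model with a lagged ever-hospitalized flag H. Stabilized weights had the fixed covariate in numerator and denominator, and H in the denominator only. The weighted Cox model was fitted with and without current H.

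Balance at months 12, 36 and 72:
- fixed covariate: SMD 0.345 before and 0.345 after weighting at each time
- H: 0.183, 0.198 and 0.195 before; -0.001, -0.002 and -0.003 after

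Shift in VE = VE with H minus VE without H, in points:

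| Analysis | Range | Most extreme case |
|---|---|---|
| First-event all-cause pneumonia | 0 to +1.6 | 15.00 - 13.41 = +1.59 |
| Recurrent all-cause pneumonia | 0 to -0.6 | 15.00 - 15.56 = -0.56 |
| First-event IPD, H partly caused by preventable pneumonia | 0 to -2.3 | 21.68 - 24.00 = -2.32 |

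In the first row H is not a consequence of the outcome; the shift is a move from a marginal to a conditional hazard ratio.

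For scale, at 97 months and 4% censoring the protocol's Table 3 gives 13 to 17 for a pneumonia VE of 15, a half-width of (17 - 13)/2 = 2 points. Table 2 gives 11 to 33 for an IPD VE of 22.5, a half-width of (33 - 11)/2 = 11 points. The extreme shifts are about 1.6/2 = 0.8 and 2.3/11 = 0.2 of those half-widths.

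**The case against.** The sentence is optional and does not say that current values would be used. SMDs are measured on baseline and pre-vaccination records only, and the code in SAP 7.2.4 drops records from 14 days after vaccination. Adding a baseline value is thus a permitted reading, and Protocol 9.7 itself lists hospitalization both as fixed at baseline and as time-varying. Respiratory virus season is set by calendar date and cannot be affected by vaccination. The rule may also seldom act: in the calculation above, weighting brought the SMD for hospitalization to about zero, and the flag was then put into the model without the trigger having been met. Finally, SAP 5.8.4 says baseline values may be poor proxies later in follow-up, so a baseline-only remedy has limits.

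Most of this stands and sets the scope of the point. It does not rescue the sentence, because nothing in the SAP confines additions to safe values and the time-updated columns are the ones to hand.

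Nor is rare triggering assured. SAP 5.8.5 mentions maximum SMDs over intervals with at least 100 vaccinated. At that floor, with many unvaccinated, the standard error of an SMD is about sqrt(1/100) = 0.1, so under perfect balance an absolute SMD above 0.1 would occur by chance in about 32% of such intervals.

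The safeguard in SAP 5.8.4, that weights are derived without looking at their effect on VE, is not extended to this choice.

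**Conclusion.** The point holds in a conditional form. The rule can change the Cox model only by adding covariates the SAP treats as time-varying. If their current values are used, the model conditions on variables that vaccination can affect and, for recurrent events, on consequences of earlier outcome events.

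A reader might infer something stronger: that the rule necessarily adds post-vaccination values and conditions on consequences of the outcome throughout. The documents do not support that. The value to be entered is left open. First-event records end at the outcome and covariates are lagged, which leaves only an edge case: an admission that crosses a 30-day boundary while a combination-code event is dated to its latest code (SAP 5.3.1). The recurrent-event VE analysis, where the stronger wording does apply, is described as optional in SAP 5.8.7, although SAP 5.8.11 lists it without that qualifier.

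The likely effect is small and mixed in sign, and every range includes zero. The sizes rest on assumed frailty, hospitalization and mediation parameters and describe what happens if the flag is added, not how often it would be. The sentence should be corrected before analysis, but nothing here suggests that it would by itself overturn a conclusion.

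**What to change.** Replace the last sentence of SAP 5.8.5 with a rule on these lines:

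1. If a time-varying covariate has an SMD above 0.1 after weighting, respecify the weight model (interactions, finer categories, time interactions) and recheck balance. State which SMD summary triggers this.
2. If outcome-model adjustment is still wanted, add only the baseline value of that covariate, never a value after vaccination. Respiratory virus season may be exempt.
3. Make the choice before VE is seen, as already planned for the weights, and report VE with and without the added term.
4. Note that fixed covariates are expected to stay imbalanced after stabilized weighting and are handled by their presence in the Cox model.

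The cost is SAP wording and at most another pass of weight fitting. The limitation is that a baseline value may not fully remove imbalance that arises late in follow-up; reporting both estimates, with the remaining SMDs, makes that visible.

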#### **5.8.6. Incidence Rates**

Incidence rates will be reported using first episodes only and again after including recurrent episodes of the same type. Crude incidence rates and 95% CIs will be presented as episodes per 100,000 person-years by PCV13 vaccination status for each outcome overall as well as annually and during time periods of interest (0-3, 3-5 and 5-7 years).

For incidence rates based on first episodes only, the total unvaccinated person-time will be calculated as time from index date to the earliest of the following: outcome, 13 days after their PCV13 vaccination, death, end of health plan enrolment or end of study period. The

total vaccinated person-time will be calculated as time from 14 days after their PCV13 vaccination date or index date, if they were vaccinated more than 13 days before the end of the baseline period, to the earliest of the following: outcome, death, end of health plan enrolment or end of study period.

For incidence rates including recurrent episodes of the same type (separated by at least 90 days), the total unvaccinated person-time will be calculated as time from index date to the earliest of the following: 13 days after their PCV13 vaccination, death, end of health plan enrolment or end of study period. The total vaccinated person-time will be calculated as time from 14 days after their PCV13 vaccination date or index date, if they were vaccinated more than 13 days before the end of the baseline period ,to the earliest of the following: death, end of health plan enrolment or end of study period. Person-time will exclude any time the patient is not at risk, i.e. the first 89 days after an episode. Cluster robust standard errors will be used in the calculation of 95% confidence intervals to account for multiple events per patient.

#### **5.8.7. Vaccine Effectiveness**

Crude PCV13 VE percentages will be estimated based on  $(1-HR) \times 100$ , where HR is obtained from unadjusted Cox models for first episodes for each outcome. VE percentages will also be obtained from marginal structural Cox models (Cox-MSM) after applying the IPT and the IPT\*IPC weights. As the numerators for the stabilized weights will include the index-fixed covariates, those covariates will also be included in the Cox-MSM for the outcomes [9]. Cluster robust standard errors will be used to account for the multiple records per patient. The proportional hazards assumption will be assessed graphically with the inspection of Schoenfeld residuals.

To explore potential changes in VE over time, HRs may also be generated during specific time periods using piecewise Cox models. The time periods will be 0-3 years (0 to 1079 days), 3-5 years (1080 to 1799 days), 5-7 years (1800 to 2549 days).

VE may also be assessed for recurrent events using the Andersen-Gill (AG) model [11]. For each outcome, subsequent events will be of the same type, e.g., in the analysis of IPD it will be assumed that a patient is only at risk for future IPD events. The VE is assumed constant across the recurrent events.

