4. ABSTRACT

Title	Assessment of PCV13 vaccine effectiveness among people with HIV
Rationale and background	
People living with HIV (PLWH) are at increased risk of pneumococcal infections. A recent meta-analysis shows that in the era of advanced antiretroviral therapy, the incidence of invasive pneumococcal disease (IPD) in PLWH is approximately 30 times higher when compared with the general population [1]. Even with timely and effective treatment, the case fatality rate of IPD is at least 8% in PLWH [2] and up to 25% of PLWH experience recurrent episodes of IPD in the subsequent 12 months [3].
 
International guidelines recommend pneumococcal vaccination for immunocompromised individuals [4] and previous research has shown that the pneumococcal conjugate vaccine (PCV) is safe and immunogenic in PLWH [5-8]. Studies have assessed the clinical efficacy/effectiveness of PCV in adults, but patients with immunocompromising conditions or treatments were either excluded from the studies, or vaccine effectiveness (VE) estimates were calculated overall and not specifically among PLWH or among people with other immunocompromising conditions [9, 10].
 
Given the lack of PCV13 VE data in immunocompromised adults, this study was designed to estimate PCV13 VE against pneumococcal disease in PLWH aged ≥ 18 years, overall and, if feasible, at 3, 5, and 7 years after vaccination.

Research objectives	
The primary objectives include:
 
1. Estimate vaccine effectiveness (VE) of PCV13 for invasive pneumococcal disease (IPD) among people living with HIV (PLWH) ≥ 18 years of age, overall and, if feasible, at 3, 5, and 7 years of follow-up2. Estimate VE of PCV13 for pneumococcal pneumonia among PLWH ≥ 18 years of age, overall and, if feasible, at 3, 5, and 7 years of follow-up3. Estimate VE of PCV13 for all-cause pneumonia among PLWH ≥ 18 years of age, overall and, if feasible, at 3, 5, and 7 years of follow-up 
The secondary objectives of this study are to:
 
1. Estimate VE of PCV13 for pneumococcal pneumonia or pneumonia with unspecified causes among PLWH ≥ 18 years of age, overall and, if feasible, at 3, 5, and 7 years of follow-up

	
2. Estimate VE of PCV13 for pneumonia with unspecified causes among PLWH ≥ 18 years of age, overall and, if feasible, at 3, 5, and 7 years of follow-up

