9.7. Data Analysis

Cox proportional hazards models will be used to estimate the hazard ratio (HR) for each outcome comparing vaccinated PLWH with unvaccinated (no PCV13) PLWH. To explore potential changes in VE over time, HRs will also be generated during specific time periods (0-3, 3-5, 5-7 years of follow-up) using piecewise Cox regression models, if there is adequate sample size. All models will be adjusted for time-fixed and time-varying covariates of interest using inverse probability of treatment weighting. The time-fixed covariates of interest include sex, age, payor, SVI, previous pneumonia infection, and hospitalization and will be measured during the baseline period. The time-varying covariates include risk factors for pneumonia (alcoholism, asplenia, asthma, chronic heart disease, kidney, liver, and lung diseases, cigarette smoking, diabetes, immunosuppressive conditions and medications, and sickle cell disease), annual physical exams, annual influenza vaccine, hospitalization, opportunistic infections, ART adherence, annual CD4 and viral load laboratory tests, and an indicator for respiratory virus season.

VE will be calculated as 1 minus the estimated HR for each outcome.

We will conduct two sets of analyses for each outcome. In the first set, we will examine the first event for each outcome and in the second set, all recurrent outcome events during follow-up will be included. In the first set of analyses, unvaccinated (no PCV13) PLWH will be followed from index date until the earliest occurrence of the following: outcome, PCV13 vaccination, death, end of health plan enrollment, or end of study period, and vaccinated PLWH will be followed from 14 days after vaccination date, or index date if vaccinated during the baseline period, until the earliest occurrence of outcome, death, end of health plan enrollment, or end of study period. In the second set of analyses unvaccinated (no PCV13) PLWH will be followed from index date until the earliest occurrence of PCV13 vaccination, death, end of health plan enrollment or end of study period and vaccinated PLWH will be followed from 14 days after vaccination date, or index date if vaccinated during the baseline period, until earliest occurrence of death, end of health plan enrollment, or end of study period.

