### 3. RATIONALE AND BACKGROUND

People living with HIV (PLWH) are at increased risk of pneumococcal infections, but there is a lack of data on 13-valent pneumococcal conjugate vaccine (PCV13) vaccine effectiveness (VE) in PLWH.

The purpose of this study is to estimate PCV13 VE against pneumococcal disease in PLWH aged  $\geq 18$  years, overall and, if feasible, at 3, 5, and 7 years of follow-up. The primary outcomes of interest are invasive pneumococcal disease (IPD), pneumococcal pneumonia and all-cause pneumonia.

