### 5.5. Treatment Labels

Information on PCV13 vaccination status will continue to be collected on and after index date and will therefore be treated as a time-varying exposure. PLWH in the study will be assigned to 'PCV13 Vaccinated' or 'PCV13 Unvaccinated' according to their vaccination status by each person-time record during the follow-up. Individuals will be considered vaccinated from 14 days after their PCV13 vaccination date till the remainder of their follow-up.

National Drug Codes (NDC) and Current Procedural Terminology® (CPT) codes used to identify PCV13 receipt are listed in Appendix Table 7.3.

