#### **5.8.9. Eligibility, Demographic, Clinical and Exposure Characteristics**

The number and percentage of patients meeting the eligibility criteria will be reported in a subject evaluation table overall and by index calendar year.

Descriptive statistics will be used to summarize patient demographics and clinical characteristics of all PLWH using values at index date by vaccination status by the end of the baseline period. Overall SMDs will be presented before and after IPTW. SMDs at the end of each year since follow-up will also be tabulated.

Summaries of the overall follow-up time will be presented and calculated as time from index date to the earliest of death, end of health plan enrollment, or end of study period.

The number of patients who receive PCV13 by the end of the overall follow-up will be reported. Kaplan-Meier analysis will be used to summarize the percentage of persons who receive PCV13 by the end of each year of follow-up from index date. Patients will be censored at the earliest of the following: death, end of health plan enrollment, or end of study period.

The overall distributions of the IPT, IPC and IPT\*IPC weights will be summarized by vaccination status. To graphically assess the IPT weights over time a plot of the distributions of the log-transformed stabilized weights may also be presented at regular (e.g. six-monthly) intervals during the follow-up.

The above analysis will be repeated by the subgroups stated in Section 5.2.3.

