### 7.2. Appendix B: R Example Code

#### 7.2.1. Example Data Formats for First Event and Recurrent Events

Example dataset for time to first outcome:

ptid	tstart	tstop	pcv13	ipd	x1	x2	xt1	xt2	censor	endfu
1001	-1	0	0	0	1	0	0	0	0	87
1001	0	30	0	0	1	0	0	0	0	87
1001	30	60	1	0	1	0	1	0	0	87
1001	60	87	1	0	1	0	1	0	1	87
1002	-1	0	0	0	0	0	0	0	0	45
1002	0	30	0	0	0	0	0	1	0	45
1002	30	45	0	1	0	0	1	1	0	45

Example dataset including any subsequent outcomes:

ptid	tstart	tstop	pcv13	ipd	x1	x2	xt1	xt2	censor	endfu2
1001	-1	0	0	0	1	0	0	0	0	87
1001	0	30	0	0	1	0	0	0	0	87
1001	30	60	1	0	1	0	1	0	0	87
1001	60	87	1	0	1	0	1	0	1	87
1002	-1	0	0	0	0	0	0	0	0	106
1002	0	30	0	0	0	0	0	1	0	106
1002	30	45	0	1	0	0	1	1	0	106
1002	45	60	0	0	0	0	1	1	0	106
1002	60	84	0	1	0	0	1	1	0	106
1002	84	90	0	0	0	0	1	1	0	106
1002	90	106	0	0	0	0	1	1	0	106

Where:

- *ptid*: patient identifier
- *tstart*: first day of interval. -1 represents baseline period
- *tstop*: last day of interval
- *pcv13*: binary indicator for time-varying PCV13 vaccination status (exposure)
- *ipd*: binary indicator for IPD event (outcome)
- *x1, x2, ..., xn*: time-fixed confounders
- *xt1, xt2, ..., xtn*: time-varying confounders
- *censor*: binary indicator for censoring event

- *endfu*: last day of follow-up up to any first event
- *endfu2*: last day of follow-up

For binary variables, 1 indicates Yes, 0 indicates No. Note, all variables in dataset must be numeric for the *ipwtn* function.

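### The 0-3, 3-5 and 5-7 year VE windows are counted from index, not from vaccination, so they do not measure durability and would understate waning

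*SAP*

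**What the plan says.** The two documents use two different clocks.

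- The Protocol abstract (section 4) and section 7 describe VE "overall and, if feasible, at 3, 5, and 7 years after vaccination".
- The numbered objectives (Protocol 8, SAP 4) and the purpose statement in SAP 3 use another anchor: "overall and, if feasible, at 3, 5, and 7 years of follow-up".
- Protocol 9.7 says "HRs will also be generated during specific time periods (0-3, 3-5, 5-7 years of follow-up) using piecewise Cox regression models" but does not say where the clock starts.
- SAP 5.8.7 gives the cut points: "The time periods will be 0-3 years (0 to 1079 days), 3-5 years (1080 to 1799 days), 5-7 years (1800 to 2549 days"). The code in SAP 7.2.5 settles the origin. It cuts on `tstart`, which SAP 7.2.1 defines as "first day of interval. -1 represents baseline period", and SAP 5.8.4 runs the 30-day intervals from index.
- Exposure is a single 0/1 state. SAP 5.5 says: "Individuals will be considered vaccinated from 14 days after their PCV13 vaccination date till the remainder of their follow-up".
- The plan expects vaccination during follow-up. SAP 5.8.9 reports the "percentage of persons who receive PCV13 by the end of each year of follow-up from index date", and SAP 5.8.5 checks pre-vaccination balance "at the end of each year of follow-up (at 360, 720, 1080, 1440, 1800, 2190, 2550, 2910 days").

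Neither document contains a term for time since vaccination.

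**The concern.** SAP 5.8.7 gives exploring change in VE over time as the reason for the windows, and the plan names possible waning when it restricts the diagnosis-year strata to three years. If waning depends on time since vaccination, a window five to seven years after index answers a different question. Someone vaccinated in year 4.5 enters it as a fresh vaccinee and is pooled with someone vaccinated during baseline.

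If protection fades, the later windows would generally show more VE than remains at that distance from vaccination. A 5-7 year estimate that still looks protective would be read as durable protection, which no specified analysis estimates. All-cause pneumonia is the outcome most exposed, because its later window can be precise enough for the confidence interval to exclude 0.

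**Working it through.** **1. The plan's own figures.** No stated number is in dispute. The nearest is Protocol Table 2 (IPD, VE 7.5%, 4% censoring): 837 events at 36 months and 1492 at 97 months. The 97-month count cannot be rebuilt exactly because the entry distribution is not given. Simple exponential times without staggered entry give 2137-2196. This is not shown to be an error. Retention was therefore calibrated to Table 2 (at VE 22.5%: 817/1452 events at 4% censoring, 752/1224 at 10%). The calibrated model then gives about 37,900-38,100 all-cause pneumonia events at 4% censoring, against 38,176 in Table 3.

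**2. Was uptake spread over follow-up in the sponsor's simulation?** Use var(log HR) = 1/[D·p(1-p)], where D is events and p the vaccinated share of events.

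- 36 months, CI -12% to 25%: SE = [ln 1.12 - ln 0.75]/3.92 = 0.1023; p(1-p) = 1/(837 × 0.1023²) = 0.114; p = 13%.
- 97 months, CI -5% to 19%: SE = [ln 1.05 - ln 0.81]/3.92 = 0.0662; p(1-p) = 1/(1492 × 0.0662²) = 0.153; p = 19% (17-21% allowing for rounding).
- If all 32% were vaccinated by index: p = 0.32 × 0.925/(0.32 × 0.925 + 0.68) = 30%.

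The implied shares are well below 30% and rise with time, so the sponsor's simulation spread vaccination over follow-up.

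**3. Mix within the 5-7 year window (days 1800-2549).** Inputs from Protocol 9.5: N = 175,000, 32% vaccinated, up to 97 months, 4% or 10% annual censoring. Assumed: 0-20% of the cohort vaccinated by index, then a constant rate solved to reach 32%.

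| Vaccinated by index | <3 y since vaccination | 3-<5 y | ≥5 y |
|---|---|---|---|
| 0% | about 45% | about 38% | about 17% |
| 20% | about 21% | about 15% | about 64% |

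With the uptake rate four times higher or lower in the first two years, the <3 year share ranges over 10-64% and the ≥5 year share over 6-71%.

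**4. What the window would show.** Approximately, window VE = Σ (share × VE at that time since vaccination). The top of each planned VE range is used; the decline is illustrative.

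- IPD, 22.5/11.25/0%: 0.45 × 22.5 + 0.38 × 11.25 = 14.4%; 0.21 × 22.5 + 0.15 × 11.25 = 6.4%. True value from 5 years: 0%. Over the wider uptake patterns the range is 4-18%. The 3-5 year window shows 14-20% instead of 11.25%.
- All-cause pneumonia, 15/7.5/0%: 0.45 × 15 + 0.38 × 7.5 = 9.6%; 0.21 × 15 + 0.15 × 7.5 = 4.3%. True value from 5 years: 0%. The unweighted 95% CI at 4% censoring is about 4% to 15% with nobody vaccinated by index, and -2% to 10% with 20%.

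**5. Check by patient-level simulation** (6 million persons, rate ratios stratified by 30-day index interval, all-cause pneumonia, truth 15/7.5/0%):

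| Vaccinated by index | Windows from index | Categories of time since vaccination |
|---|---|---|
| 0% | 15.0 / 13.4 / 10.2 | 15.1 / 8.4 / 0.7 |
| 20% | 15.3 / 9.5 / 4.4 | 15.7 / 7.8 / 0.3 |

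Time since vaccination recovers the truth within simulation error; the index windows do not.

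**The case against.** The strongest reply is that the plan meets its numbered objectives: all of them say years of follow-up, and the windows deliver that. The after-vaccination wording is one sentence, used in the abstract and in section 7. The piecewise analysis is also optional and exploratory. This stands, and it is why the point does not touch overall VE or the primary estimates. It does not remove the conflict with the stated design purpose.

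The size is also open to challenge.

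- **Low-end VE.** At the bottom of the planned ranges, with the same proportional decline, the 5-7 year window shows only about 1.5-3% for all-cause pneumonia (from 5%) and 2-5% for IPD (from 7.5%), and every interval includes 0.
- **Conditional precision.** Even from 15%, with constant uptake, the all-cause interval excludes 0 only if about 10% or fewer of the cohort are vaccinated by index. Weighting would widen it further.
- **Early uptake.** With 30% vaccinated by index, the all-cause window shows about 1%. If all vaccination falls in baseline, the IPD 3-5 year window is 10.2-10.5%, slightly below 11.25%. The upward direction is therefore not universal, although Table 2 does not point to such early uptake.
- **Waning itself.** The decline to zero is hypothetical. The cited older-adult trial saw efficacy persist over a mean of 4 years, but it excluded immunocompromised patients.

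These points limit how large the distortion may be. None makes the index windows a measure of durability. The planned uptake, annual incidence and person-time summaries do not show time since vaccination within each window.

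**Conclusion.** The concern holds. The windows estimate VE by time since index. The abstract and section 7 promise VE by time since vaccination, and no specified analysis supplies it. If VE wanes, the later windows dilute the decline without hiding it entirely. Under constant uptake with 0-20% vaccinated by index, the 5-7 year window shows 6-14% for IPD and 4-10% for all-cause pneumonia where the true value is 0%.

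These sizes rest on assumed uptake timing, on the top of the planned VE ranges, on an illustrative waning curve, and on early and late vaccinees waning alike. Calendar-time or serotype changes could also move the window hazard ratios either way. The change should be made, but the overall VE analysis is sound on this point without it.

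**What to change.** 1. Add, as the waning analysis, a time-updated exposure: unvaccinated; 0-<3, 3-<5, 5-<7 and ≥7 years since vaccination date plus 14 days. For people vaccinated in baseline, count from their vaccination date, not from index. Keep time since index as the Cox time axis and use the same IPT and IPT*IPC weights; the IPT weights are already constant after vaccination.
2. Keep the existing windows as a proportional-hazards check, labelled as time since index.
3. Report the distribution of time since vaccination within each window.
4. Use one wording in the abstract, section 7 and the objectives.

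At the least, do items 3 and 4 and label the windows.

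The cost is wording plus one recoded variable; the dates are already held. The drawback is precision. At constant uptake and a constant IPD VE of 22.5%, the 5-<7 year category would hold about 15-43 vaccinated events, with an unweighted CI from -8% to 44% at best to -34% to 55% at worst. The planned 5-7 year window is also wide, about -4% to 42% at best and -10% to 45% at worst. For all-cause pneumonia the category would hold about 420-1,230 vaccinated events, with a CI of about ±6 to 11 points. Weighting would widen all of these. The existing feasibility clause covers the IPD case.
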